**Figure 1: Experimental design and patient flow**

**Table 1. Inclusion and exclusion criteria**

Inclusion criteria:	Exclusion criteria:

1. First episode of stroke;

2. Aged 60 or more;

3. Muscle strength of grade <5 and >2 based on manual muscle testing of the hand or fingers on the paretic side;

4. Time since stroke onset > 1 month and < 6 months;

	

1. Mini Mental State Test score ≤ 24;

2. Mental illness;

3. Contra-indications to rTMS according to guidelines formulated by Wassermann (e.g., intracranial implants, epilepsy, cardiac pacemaker, implanted medication pumps);

4. Unstable cardio-pulmonary condition.

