#### 2.2.2. Sample size estimation

The sample size was estimated from previously published data on one of the primary outcome measures, the motor-evoked potential (MEP). In a study involving a sample of 20 people by Takeuchi et al. (Takeuchi et al. 2008), a significant improvement in MEP was shown in the intervention group. The estimated effect size was about 0.6. Based on this, with the power set at 90% and  $p < 0.05$ , the minimum estimated sample size would be 22. When considering a 10% attrition rate, the minimum sample size required would be 24 individuals with stroke.

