## 2.4. Intervention protocol

The experimental group received 10 sessions of rTMS treatment and a structured upper limb training program, whereas the sham control group received sham rTMS and structured upper limb training only. In addition, both groups received the structured upper limb physiotherapy training program 2 sessions per week for another 10 weeks after the 10 sessions of rTMS or sham stimulation had ended. The details of the treatment protocol for each group are described below.

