#### 2.4.2 Experimental group

The participants in the experimental group underwent transcranial magnetic stimulation over hotspot at contralesional M1 region on weekdays over a 2-week period (i.e., 10 sessions), using a Magstim Rapid Stimulator (Magstim Company, Whitland, UK). We used a figure-of-eight coil (each loop 70 mm in diameter) for delivering the stimulation. The stimulation protocol of rTMS used was at a low frequency of 1 Hz with a stimulus intensity of 90% of rMT for a total of 1200 pulses in each session. This low-frequency protocol was adopted because the stimulation parameters were shown to result in down-regulation of motor cortical excitability over the contralesional cortex (Boggio et al., 2006). For frequencies from 0.2 to 1 Hz (low frequency), which favor the manifestation of the long-lasting inhibitory phase, may lead to cortical inhibition. Conversely, frequencies >2 Hz can mask the inhibitory phase of the preceding pulse,

thereby maintaining the neurons in a state of excitation (Moliadze et al. 2003). A meta-analysis by Zhang et al. (2017) found that low frequency rTMS was more beneficial than high frequency rTMS, and that rTMS administered to the contralesional hemisphere elicited better improvements in upper limb motor recovery than when applied to the lesioned hemisphere (Zhang et al., 2017).

The participants in the experimental group also underwent structured upper limb exercise training conducted by a registered physiotherapist in Queen Elizabeth Hospital. Each participant exercised at his or her own pace and was encouraged to perform the exercise continuously for thirty minutes in each session. In the treatment sessions during the first 2 weeks, the participants performed the 30-minute exercise training immediately after the brain stimulation. For the subsequent 10 weeks, the participants continued to receive exercise training twice per week. In each exercise session, two modes of exercises with 15 minutes for each were offered to improve task performance and dexterity of the paretic upper limb. The specific exercises included: 1. reach and grasp exercises: stacking cones or placing cones, and 2. fine motor control exercises of the hand .

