### 2.6.1. Measures of body structures/function

#### 2.6.1.1 *Fugl-Meyer assessment (FMA)*

In the upper-extremity portion of the Fugl-Meyer Motor Assessment Scale (FMA) (Appendix VIII), 25 test items included measurement of movement, coordination, and reflex action of the different parts of the paretic upper extremity. The score could range

from 0 to 66. Better motor function was reflected by a higher FMA score (Fugl et al., 1975). The FMA scores have been shown to have high construct validity, test-retest and interrater reliability (Platz et al., 2005). The minimum clinically important difference MCID of FMA was 5.2 points for the upper extremity portion (Wagner et al., 2008).

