## 2.8. Statistical analysis

The software package SPSS 21.0 for Windows (IBM, Armonk, NY, USA) was used for statistical analysis. The demographic characteristics of the participants and outcome variables at baseline were compared using the Chi-square test (for nominal data), Mann-Whitney U test (for ordinal data), and independent t-test (for continuous

data). Next, for each continuous outcome measure (FMA, MEP, GS, ARAT, B&B, RT), a  $2 \times 3$  two-way repeated measures ANOVA (mixed design; within-subject factor: time; between-subject factor: group) was used to determine whether there was a significant treatment effect on each of the outcome variables (i.e., significant group  $\times$  time interaction effect). If any substantial difference was found in particular baseline characteristics between the two groups, the variables would be entered as covariates in the above ANOVA model. Post-hoc analysis was then performed to examine the within-group changes over time using paired t-tests and between-group differences in change score at week 2 and week 12 using independent t-tests.

For analysis of the NHPT, because the failure cases were assigned a value of 600s, non-parametric statistics was used. Friedman test and post-hoc Wilcoxon test were used to examine the within-group changes over time, while Mann-Whitney U test was used to examine the difference between the two groups at week 2 and 12.

Next, for those clinical outcome variables that yielded a significant treatment effect (i.e., significant group  $\times$  time interaction effect), Pearson's product moment correlation coefficients were used to determine the degree of correlation between changes in these variables and those in MEP on both sides.

Intention to treat analysis was first conducted. Any missing data would be substituted using the last-observation-carried-forward (LOCF) method. This was followed by on-protocol analysis, in which only those participants who completed all outcome assessments were included.

The alpha was set at 0.05, except for post-hoc tests where the alpha was adjusted to 0.025 (i.e., Bonferroni correction) because of the 2 comparisons made (within-group analysis: baseline Vs week 2; week 2 Vs week 12; between-group comparison of change score: week 2 and week 12).

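### LOCF in the intention-to-treat analysis can bias the week-12 contrast modestly in either direction, and the completer analysis is not a safe check on it

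*Combined protocol and SAP*

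**What the plan says.** Section 2.8 puts the intention-to-treat analysis first and gives one rule for gaps in it: "Any missing data would be substituted using the last-observation-carried-forward (LOCF) method". The second analysis is called on-protocol, and in it "only those participants who completed all outcome assessments were included". No other missing-data method or sensitivity analysis is planned.

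Outcomes are measured at baseline, after stimulation (week 2) and at week 12 (section 2.5.1). Training does not stop at week 2. Section 2.4 says that "both groups received the structured upper limb physiotherapy training program 2 sessions per week for another 10 weeks", and section 2.4.2 repeats for the experimental arm: "For the subsequent 10 weeks, the participants continued to receive exercise training twice per week". The within-group post-hoc comparisons in section 2.8 are "baseline Vs week 2; week 2 Vs week 12". Section 2.2.2 plans the sample size with "When considering a 10% attrition rate", and arrives at 24.

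**The concern.** LOCF assumes that nothing changes after the last observed visit. This plan gives reason to doubt that. "Time since stroke onset" at entry is between 1 and 6 months (Table 1), both arms are still being trained up to week 12, and the plan itself tests for change between weeks 2 and 12. A participant who leaves after week 2 is nevertheless entered with exactly zero change over that interval.

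Two results are affected. The within-group gain from week 2 to week 12 is shrunk. The week-12 between-group contrast, and through it the group-by-time interaction, is shifted whenever loss or later gain differs between arms. The shift has no fixed direction, so LOCF cannot be defended as conservative. The completer analysis would be the natural cross-check, but it has a bias of its own when loss is related to how well a patient did early on.

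**Working it through.** **Inputs from the documents.** Minimum sample 22, attrition 10%, final sample 24 (section 2.2.2); allocation 1:1 (section 2.3), so 12 per arm; FMA MCID, from section 2.6.1.1: "The minimum clinically important difference MCID of FMA was 5.2 points"; alpha 0.05, and 0.025 for post-hoc tests (section 2.8).

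**Assumed, because the documents do not give them.** Later (week 2 to 12) FMA gain of 2.6 to 5.2 points, i.e. half to one MCID; the split of losses between arms; all SDs and correlations.

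**Expected losses.** 22 × 1.10 = 24.2, stated as 24. The plan's allowance is therefore about 2 of 24.

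**Bias when loss is after week 2 and unrelated to outcome.** Each lost participant's later gain is set to zero, so an arm's week-12 mean change falls by p·g. For rTMS minus sham:

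bias = pS·gS − pE·gE

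| Losses (rTMS, sham) | Later gain (rTMS, sham) | Bias, FMA points |
|---|---|---|
| 1, 1 | 5.2, 5.2 | 0 |
| 1, 1 | 5.2, 2.6 | (1/12)(2.6) − (1/12)(5.2) = −0.22 |
| 0, 2 | 2.6, 2.6 | (2/12)(2.6) = +0.43 |
| 0, 2 | 5.2, 5.2 | (2/12)(5.2) = +0.87 |
| 2, 0 | 5.2, 5.2 | −(2/12)(5.2) = −0.87 |

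0.87/5.2 = 17% of the MCID. A participant who misses both follow-up visits has baseline carried forward, and total gain then replaces later gain in the formula: with an assumed total gain of 5.2 to 10.4 points and two of 12 lost in one arm, the bias is 0.87 to 1.73.

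**How often the split is uneven.** Two random losses fall in the same arm with probability 2·C(12,2)/C(24,2) = 132/276 = 48%. Averaged over random splits, the bias is −(gE − gS)/12, which is zero when later gain is equal.

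**Within-group later gain.** It shrinks by p: 1/12 = 8.3% or 2/12 = 16.7%.

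**Test size.** Simulation with 20,000 trials per scenario, 12 per arm, no true effect, SD 1, compound-symmetric correlation 0.8, early gain 0.5 SD, loss at week 12 only:

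| Loss | Later gain (SD) | Week-12 t-test at 0.025 | Interaction at 0.05 |
|---|---|---|---|
| Two of 24 at random | 0.5 to 1.0 | 2.4% to 2.7% | 4.9% to 5.3% |
| One per arm | 0.5 to 1.0 | 1.4% to 2.3% | 3.1% to 4.5% |
| Two sham at random | 0.22 to 0.43 | 2.5% to 2.9% | 4.9% to 5.6% |
| Two sham at random | 0.5 to 1.0 | 2.9% to 3.6% | 5.7% to 6.9% |

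A gain of 0.22 to 0.43 SD is 2.6 to 5.2 points at an assumed SD of 12.

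**When loss depends on early recovery.** Suppose the two sham patients with the least early gain are lost. Let early and later change each have variance 0.4 (SD 0.632) and correlation r. The two lowest of 12 normal values lie on average 1.37 SD below the mean, so the lost patients' early change is 1.37 × 0.632 = 0.87 below average, and their later change is expected to be 0.87r below average. Then:

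- LOCF bias = (2/12)(g − 0.87r)
- completer bias = −(2/10)(0.87)(1 + r)

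Results in SD units:

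- r = −0.5 (what compound symmetry at 0.8 implies), g = 0.5 to 1.0: LOCF +0.16 to +0.24, completer −0.09. Opposite signs.
- r = +0.5, g = 0.22: LOCF (1/6)(0.22 − 0.43) = −0.04, completer −0.26. Same sign.
- r = +0.7, g = 0.43: LOCF −0.03, completer −0.30. Same sign.

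The documents do not say which of these applies.

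**The case against.** The strongest reply is that little is at stake. Over random losses the bias averages zero when later gain is equal, and both tests hold their size; one loss per arm makes LOCF conservative. Both losses must fall in one arm to reach even 17% of the MCID. The highest LOCF interaction rate under random loss, 6.9%, needs a later gain of 1.0 SD, which is 12 FMA points at an SD of 12, more than twice the top of the assumed range. The week-12 t-test is also post hoc to the interaction. All of this stands and sets the weight of the point.

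Three stronger readings are tempting, and the documents support none of them.

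- A reader might infer that LOCF seriously inflates false positives. At the planned attrition it does not, and no trajectory, SD or loss pattern is documented from which a larger effect could be derived.
- A reader might infer that LOCF and completers err in opposite directions and so bracket the truth. The sign depends on the correlation between early and later change and on the later gain, neither of which is stated.
- A reader might infer that NHPT and MEP need new missing-data rules as part of this point. NHPT failure (600 s, section 2.6.2.2) is already distinct from a missing value, and the zero assigned to an untriggered MEP raises the same question with or without LOCF. Relabelling the on-protocol analysis is a preference, since section 2.8 already defines it as completers.

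The reply does not rescue LOCF as a method. It is not reliably conservative, and its planned companion can be biased too.

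**Conclusion.** The method point holds with high confidence: the intention-to-treat rule assumes no change over an interval in which both arms are being treated and the plan looks for change. Its effect is modest and conditional: 0 to 0.87 FMA points in either direction for up to two losses after week 2, more if loss is higher or comes earlier. These sizes rest on assumed gains, SDs and correlations and should be read as a range, not a prediction. Because completers-only is biased when loss depends on early recovery, in a direction that cannot be known in advance, agreement between the two planned analyses would not show that missing data did no harm. This is a cheap improvement, not a threat to the trial's validity.

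**What to change.** For the continuous outcomes, make the intention-to-treat analysis a likelihood-based mixed model for repeated measures. It should use all randomised participants and all observed visits (baseline, week 2, week 12), with unstructured covariance, the group-by-time interaction, week-2 and week-12 contrasts, and small-sample degrees of freedom. Carry over any baseline covariates that section 2.8 would add for imbalance. Keep LOCF and the completer analysis as sensitivity analyses.

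The cost is SAP wording and a little more analysis work. In simulation, for a given split of losses, the SD of the likelihood-based estimate was about 4% to 6% larger than under LOCF. The model relies on data being missing at random, i.e. on missingness depending only on observed data. Its bias was zero in the simulated scenarios, but all of them met that assumption by construction, so they do not show protection when it fails.

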**Figure 6: Measurement schedule**

## 2.6 Outcome measures

A battery of assessment tools was chosen to evaluate the participants across the domains of International Classification of Function, Disability, and Health endorsed by the World Health Organization (i.e., body functions/structures, activity and participation WHO Disability Assessment Schedule (WHO 2010). The upper-extremity portion of the Fugl-Meyer Motor Assessment Scale (FMA) (Fugl-Meyer et al., 1975) was the primary behavioral measure outcome of arm function, whereas the motor evoked potential (MEP) was the primary physiological measure. Secondary measures included grip force (Takeuchi et al., 2008), the Action Research Arm Test (ARAT), the Nine Hole Pegboard test (NHPT), the Box and Block test, the reaction time test, and the Stroke Impact Scale (SIS).

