#### *2.6.1.2 Motor evoked potential (MEP)*

To obtain the MEP of the FDI, EMG activity was measured using silver–silver chloride (Ag-AgCl) electrodes placed on the skin overlying the FDI. The peak-to-peak MEP amplitude was recorded, which reflects cortical excitability (Malcolm et al., 2007) (Figure 7). Ten averaged MEPs evoked from the M1 hotspot on both the ipsilesional and contralateral sides at 120% rMT were recorded using the Magstim 200 (Magstim Company, Whitland, UK). If the EMG could not be triggered at 100% of the resting motor threshold, the MEP was defined as “cannot be triggered” and set at zero.

If the MEP was absent when stimulating the lesioned hemisphere by the stroke, the motor hotspot was defined as being symmetrical to the contra-lesional hemisphere. The signal was amplified, bandpass filtered (1-5k Hz), and digitized for off-line analysis with ADC sampling rate of 3kHz by a built-in EMG device in Brainsight 2 (Brainsight 2, Rogue Research Inc., Montreal, Canada).

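### Two primary outcomes (FMA and MEP) are each tested at 0.05 with no success rule; if either one can carry the conclusion, the false-positive risk is up to 9.75% (two independent tests), not 5%

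*Combined protocol and SAP*

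**What the plan says.** Section 2.6 names two primary outcomes: FMA "was the primary behavioral measure outcome of arm function, whereas the motor evoked potential (MEP) was the primary physiological measure". Section 2.2.2 confirms that MEP is not the only one: "The sample size was estimated from previously published data on one of the primary outcome measures, the motor-evoked potential (MEP"). It uses an effect size of about 0.6, 90% power and p < 0.05, from which "the minimum estimated sample size would be 22", raised to 24 for attrition.

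Section 2.8 gives every continuous outcome its own 2 x 3 mixed ANOVA, which "was used to determine whether there was a significant treatment effect on each of the outcome variables", and equates a treatment effect with a significant group x time interaction. The significance level is set in one sentence: "The alpha was set at 0.05, except for post-hoc tests where the alpha was adjusted to 0.025 (i.e., Bonferroni correction"). The reason given for the 0.025 is "because of the 2 comparisons made". The comparisons listed are baseline to week 2 and week 2 to week 12 within groups, and the change scores at week 2 and week 12 between groups.

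On the side of the MEP, section 2.6.1.2 says: "Ten averaged MEPs evoked from the M1 hotspot on both the ipsilesional and contralateral sides at 120% rMT were recorded". Section 2.8 later correlates "changes in these variables and those in MEP on both sides". Its list of outcomes for the ANOVA has MEP once, with no side.

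**The concern.** Two outcomes carry the label primary, so at least two tests can produce a primary finding, each with its own 5% chance of a false one. The plan gives no testing order, no split of alpha across the two, and no statement of whether success means either or both. The 0.025 could be mistaken for a split between two primary outcomes, but it applies only after the interaction test and only to time contrasts.

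The conclusion can turn on this. Suppose one primary interaction has p = 0.04 and the other is clearly non-significant. Under section 2.8 that is a treatment effect on a primary outcome. With the pair held at 5% by Holm or Bonferroni, it is not. The unnamed MEP side adds a choice that could be made after the results are seen.

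**Working it through.** **Inputs from the documents.** Two primary outcomes (2.6); alpha 0.05 per interaction test (2.8); two groups, 1:1 (2.3); three visits (2.5.1); effect size 0.6, 90% power, 22 before attrition and 24 after (2.2.2). The correlation between the primary outcomes is not given; 0 to 0.8 is assumed.

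**1. The plan's own figure.** Reading 0.6 as an f for the interaction, with noncentrality f²(N − 2)(3 − 1):
- N = 22: 0.36 × 20 × 2 = 14.4, on 2 and 40 df, gives power 0.915. The smallest N for 90% is 22.
- A second reading also returns 22. It takes 0.6 as an f for the between-group factor over three visits with within-person correlation 0.5: 0.36 × 22 × 3 / (1 + 2 × 0.5) = 11.88, on 1 and 20 df, power 0.906.
- Attrition: 22/0.9 = 24.4 and 22 × 1.1 = 24.2, so 24 is close to the plan's arithmetic.

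Both readings use one test at 0.05. The 22 therefore belongs to a single MEP test.

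**2. If either primary result is enough.** Chance of at least one false interaction with k independent tests: 1 − (1 − 0.05)^k.
- k = 2: 1 − 0.95² = 0.0975.
- k = 3 (only if both MEP sides are primary): 1 − 0.95³ = 0.1426.

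For correlated outcomes, simulation with 11 per arm, normal data, equal correlation 0.5 between visits, interaction F on 2 and 40 df, 40,000 runs per cell:

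| Assumed outcome correlation | 0 | 0.3 | 0.5 | 0.8 |
|---|---|---|---|---|
| Two tests, each at 0.05 | 9.7% | 9.4% | 9.2% | 7.8% |
| Three tests, each at 0.05 | 14.2% | 13.9% | 13.0% | 10.0% |
| Two tests, Holm | 4.8% | 4.7% | 4.7% | 4.1% |
| Three tests, Holm | 5.0% | 4.9% | 4.7% | 3.6% |

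Repeat runs agree within about half a percentage point. Beyond 0.8 the two-test figure keeps falling: 7.2% at 0.9 and 6.6% at 0.95. So 8% is a point on an assumed scale, not a floor.

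**3. If both are needed.** The chance that both are falsely significant cannot exceed 5%. Power is then the issue. Suppose, for illustration, that FMA also had 90% power. The chance that both succeed is 0.9 × 0.9 = 81% if independent, and lies between 1 − 0.1 − 0.1 = 80% and 90% under any dependence. FMA's actual power is not given, so the true figure is unknown.

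**4. Cost of a smaller alpha for a lone effect, 22 analysed.**

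| Reading of 0.6 | 0.05 | 0.025 | 0.0167 |
|---|---|---|---|
| Interaction f | 91.5% | 85.7% | 81.5% |
| Between-group f, three visits | 90.6% | 83.8% | 78.9% |

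The losses are 5.8 and 10.0 points on the first reading, 6.8 and 11.7 on the second. If 0.6 were a standardised mean difference between arms, 118 to 120 people would be needed for 90%, and 11 per arm would give only 26.8% at 0.05 and 17.9% at 0.025. The documents do not say which scale applies.

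**The case against.** The strongest reply is that FMA and MEP answer different questions, one about behaviour and one about physiology, and that section 2.8 asks about each outcome separately. If the trial reports two separate conclusions, each keeps its own 5% and no adjustment across them is needed. This stands as a possible reading, and it is why the 9.75% must carry its condition. It does not close the point: the documents do not say that the claims are separate, and they do not rule out a positive conclusion drawn from either one.

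A reader might also infer that the plan has three primary tests and a 14% error rate. The documents do not support this as fact. Both sides appear in the recording of MEP and in the correlation step, but the ANOVA list has MEP once and no passage plans two MEP ANOVAs. Three tests is a possibility left open by the missing side.

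The rates also assume that each ANOVA holds its own 5%. The visits are unequally spaced, MEPs that cannot be triggered are set to zero, and no sphericity correction is named. Under one illustrative covariance (between-visit correlations 0.8, 0.3 and 0.4), an uncorrected test rejects about 6.5% of the time under the null. Holm on such p-values would not guarantee 5%.

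**Conclusion.** The concern holds in conditional form. The plan has two primary outcomes, each tested at 0.05, and no rule for combining them. If either may carry the conclusion, the false-positive risk for the pair is 9.75% with independent tests and about 8% at an assumed correlation of 0.8. If both are required, the error is controlled, but the stated 90% does not describe the chance of success. If both MEP sides were primary, the either-counts figure would be 14.26%, or about 10% at correlation 0.8. All of these assume valid individual tests.

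Two stronger statements should not be made. The first is that the trial's false-positive rate simply is 8% to 14%: this drops the success rule, treats three tests as planned, and presents an assumed correlation range as a property of the plan. The second is that FMA is underpowered: its power is not justified in the documents, which is not the same as being shown to fall below 90%.

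This should be fixed, because a primary p-value just under 0.05 would be read differently under a controlled rule.

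**What to change.** **Section 2.8.** Apply Holm at a family-wise 0.05 to the primary group x time p-values.
- If a document dated before unblinding names the primary MEP side, there are two tests: the smaller p-value against 0.025, then the other against 0.05.
- If not, there are three tests, FMA and MEP on each side: 0.0167, then 0.025, then 0.05. Say that both sides are included because none was named, not because both were prespecified as primary.
- Choose no side after results are known.
- Keep the other outcomes secondary, as section 2.6 has them.

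Section 2.2.1 puts recruitment between November 2015 and December 2016, and the text is in the past tense. The addition must therefore be dated and labelled as made after recruitment, with adjusted and unadjusted p-values side by side.

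**Section 2.2.2.** State that the calculation was for one MEP test at 0.05 and that FMA was not separately powered. Name the MEP side and the scale of the 0.6.

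**Cost.** No new participants or visits are needed. At most, the MEP ANOVA is reported for each recorded side. A lone primary result with p between 0.025 (two tests) or 0.0167 (three tests) and 0.05 would no longer count as significant. Because Holm stops at the first failure, two results both between 0.025 and 0.05 would also fail. Power for a lone effect falls, by an amount that cannot be settled until the scale of the 0.6 is known.

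### A flat Bonferroni level of 0.025 within each pair of post-hoc comparisons is needlessly conservative; Holm keeps the same 5% family-wise limit and is more likely to show an effect at both weeks

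*Combined protocol and SAP*

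**What the plan says.** For the outcomes treated as continuous (FMA, MEP, grip strength, ARAT, Box and Block, reaction time), section 2.8 specifies a mixed ANOVA with two groups and three times. It "was used to determine whether there was a significant treatment effect on each of the outcome variables", and such an effect is defined as a significant interaction of group and time. The section continues: "Post-hoc analysis was then performed to examine the within-group changes over time using paired t-tests and between-group differences in change score". The between-arm tests are made for both later visits.

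The levels are given at the end of the section. An overall alpha of 0.05 applies to all tests, "except for post-hoc tests where the alpha was adjusted to 0.025 (i.e., Bonferroni correction) because of the 2 comparisons made". Two pairs are named as the reason for halving. One is the within-group pair (baseline against week 2, week 2 against week 12). The other is the "between-group comparison of change score: week 2 and week 12".

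Two further features matter here. The section does not say that the post-hoc tests are run only after a significant interaction; that condition is written only for the later correlation analysis. The Nine-Hole Peg Test (NHPT) is handled separately. It has Friedman and Wilcoxon tests within groups and Mann-Whitney tests between groups at weeks 2 and 12, with no between-arm omnibus test before them.

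**The concern.** The two between-arm contrasts carry the clinical message: whether rTMS helps at the end of stimulation, and whether the benefit is still present at week 12. Bonferroni tests each at 0.025 whatever the other shows. Once one week has been shown at 0.025, family-wise control no longer requires so strict a level for the other, so the plan gives up power without gaining any guarantee. In a trial of 24 patients, that loss falls on the claim that the effect is present at both weeks.

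**Working it through.** **Inputs.** From section 2.8: overall alpha 0.05; post-hoc alpha 0.05/2 = 0.025, which reproduces the plan's figure; two comparisons per pair. From sections 2.2.2 and 2.3: 24 patients allocated 1:1, so 24/2 = 12 per arm. From section 2.5.1: three assessments. Assumed, because the plan does not give them: two-sided tests, normal data, compound symmetry, changes measured from baseline, no dropout, and an equal arm difference at both weeks in units of the SD of change.

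**Step 1: the error guarantee.** Order the two p-values of a pair. Bonferroni rejects each one below 0.025. Holm rejects the smaller if it is below 0.025 and then, only in that case, the larger if it is below 0.05.
- Both nulls true: under either rule a false rejection requires the smaller p-value to be below 0.025. The family-wise error is therefore identical, at most 2 × 0.025 = 0.05. Simulated: 4.7% for both.
- One null true: Holm tests it at 0.05 at most, so the error is at most 0.05. With a large effect at one week, the simulated false-positive rate at the other was 4.9% with Holm, against about 2.5% with Bonferroni. Holm uses the allowance that Bonferroni leaves unspent.

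Holm rejects everything that Bonferroni rejects. It differs only when the smaller p-value is below 0.025 and the larger lies between 0.025 and 0.05; it then rejects both.

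**Step 2: dependence on the correlation between visits.** Under compound symmetry with correlation ρ and unit variance, each change from baseline has variance 2(1 − ρ) and the two changes have covariance 1 − ρ. Their correlation is (1 − ρ)/[2(1 − ρ)] = 0.5 for every ρ. With the effect in SDs of change, ρ cancels, so one table serves all values of ρ. For the same reason, varying ρ is not a sensitivity analysis.

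**Step 3: size, ungated.** Simulated trials (60,000 per row for the both-weeks columns), 12 per arm:

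| Arm difference (SD of change) | Both weeks, Bonferroni | Both weeks, Holm | At least one week, either rule |
|---|---|---|---|
| 0.6 | 8.1% | 13.3% | 31% |
| 0.8 | 19.2% | 28.3% | 50% |
| 1.0 | 35.6% | 47.4% | 70% |
| 1.2 | 55.5% | 67.4% | 85% |

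Other runs gave Holm figures up to about half a point higher (13.5%, 48% and 68% at 0.6, 1.0 and 1.2 SD).

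Cross-check at 1.0 SD: power per week is about 52.8% with Bonferroni and 58.6% with Holm. The chance of at least one week equals twice the per-week power minus the chance of both. That is 2 × 52.8 − 35.6 = 70.0% for Bonferroni and 2 × 58.6 − 47.4 = 69.8% for Holm, equal up to rounding, as Step 1 requires.

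**Step 4: size if the interaction is read as a gate.** At 1.0 SD, a significant interaction followed by Bonferroni shows both weeks in 36% of trials; followed by Holm, in 47%. The gain from Holm therefore does not depend on how the gate is read.

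**The case against.** The strongest case for the plan is that Bonferroni is valid, simple and fixed in advance, and that choosing a conservative procedure is not an error. The declared treatment effect is the interaction at 0.05, which the post-hoc rule does not touch, and the plan does not require significance at both weeks. All of this stands. It limits the consequence to the interpretation of the two weeks, but it gives no reason to prefer Bonferroni to a procedure that never rejects less under the same limit.

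A reader might infer something stronger: that the contrasts are already protected by the two-degree-of-freedom interaction test, so the 0.025 is a second payment and can be dropped. The logic is sound if a gate exists. The interaction null is exactly no arm difference in either change, so by closed testing each contrast may be tested at 0.05 after a significant interaction. Simulated family-wise error is then 4.1% with no effect at either week and 5.0% at the null week when the other effect is large. The documents do not support dropping the correction, for four reasons:
- The gate is implied by the order of the text and the label post-hoc, but it is not written. Ungated, testing each contrast at 0.05 gives a family-wise error of about 9.1%, and the 0.025 is then the only control.
- NHPT has no between-arm omnibus test that could serve as a gate.
- The same 0.025 covers the within-group pair, which the interaction test does not protect.
- Closed testing needs a valid F test, and no sphericity correction is stated. In assumed non-spherical examples the gated error at 0.05 was 4.6% to 6.4%, against 2.6% to 4.0% at 0.025.

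Nor is a drop from 48% to 36% a property of the plan. It requires an assumed difference of 1.0 SD at both weeks and all 24 patients retained. Section 2.2.2 gives an effect size of about 0.6, of unstated type and based on MEP, and allows for 10% attrition.

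**Conclusion.** The flat 0.025 controls error but is dominated by Holm under either reading of section 2.8. Over assumed arm differences of 0.6 to 1.2 SD of change, equal at both weeks, Holm raises the chance of showing both weeks by about 5 to 12 percentage points (13.3 − 8.1 = 5.2; 67.4 − 55.5 = 11.9). The chance of showing at least one week stays the same. The ordering of the two procedures needs no assumption about effect size, correlation or sphericity; the sizes rest on the assumptions listed with the inputs. This is a free improvement. It does not invalidate the planned analysis or its definition of a treatment effect.

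**What to change.** Keep the overall alpha of 0.05 and change only the post-hoc rule, for example: 'Within each pair of post-hoc comparisons (between-arm change at weeks 2 and 12, including the NHPT Mann-Whitney pair; within-group pairs) the Holm procedure is used: the smaller p-value is tested at 0.025 and, if significant, the larger at 0.05.' Naming the NHPT pair also settles whether the correction covers it, which the present text leaves unclear. The whole sentence on alpha should not be struck out, because it also sets the overall level and the rule for the within-group tests.

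An optional alternative, for the ANOVA between-arm contrasts only, is to write the gate explicitly: test the contrasts only after a significant, sphericity-corrected group-by-time test, then each at 0.05. Holm or Bonferroni must then stay for the NHPT and within-group tests. The price is that no contrast may be claimed without a significant interaction.

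Holm costs one clause, no patients and no extra data, and it can be applied by hand to the p-values that SPSS prints. The section is written in the past tense; if results are already known, the change should be reported as made afterwards, beside the Bonferroni result.
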